## 1. Introduction

### 1.1 Background

There is a drive for trainee anaesthetists to be competent in a number of common ultrasound guided blocks and proficiency is considered an important part of the anaesthetic curriculum laid out by the RCoA. Ultrasound improves the safety, efficacy and efficiency of peripheral nerve blocks. It is now the accepted standard of practice in most institutions. However, one challenge for trainers and trainees is that there is a lack of simple, readily available, evidence-based and validated methods to assess the anaesthetists' ability to identify structures using ultrasound. The development of a validated tool to evaluate proficiency in ultrasound-guided regional anaesthesia (UGRA) interpretation would improve the uniformity and consistency of assessment in the UK.

Validated tools for assessment of ultrasound may be even more valuable with the recognised advantages and increased use of regional anaesthetic techniques during the COVID-19 pandemic. Possible advantages to anaesthetists and hospitals include reduced risk of transmission to staff, and preservation of drugs and personal protective equipment required during critical care of COVID-19 patients. These patients may also benefit from avoiding the further cardiorespiratory strain of undergoing a general anaesthetic. All patients may also experience improved postoperative pain relief (thereby also minimising direct contact with care givers), reduced time in recovery and earlier hospital discharge.

**Legal defensibility** is a concept that is central to any assessment tool. There needs to be confidence in the processes used to construct the assessment tool and that the outcomes of the test reflect the participant's ability. The application of rigorous **psychometric principles** is essential to achieving the high standard of **validity** and **reliability** of an assessment required by educational institutions. Anaesthetists seeking certification that is not based on a validated assessment method could give rise to the question of ethical injustice and possibly expose an organisation to legal challenges. On the other hand, anaesthetists that are inappropriately certified may risk patient safety.

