The assessment tool must measure what it is supposed to measure. Firstly, **face validity** will be ensured by our participants judging the questions as easy to understand and the ultrasound video quality as representative of clinical practice. The **content validity** of the assessment tool will be verified by a panel of experts who will be asked to assess its relevance to regional anaesthesia by matching it to the RCoA curriculum. Next, the **construct validity** of the assessment will be evidenced by anaesthetists with more regional anaesthesia experience achieving higher ultrasound interpretation scores. The stages of training in our assessment tool will include consultants and will also be based on the new 2021 RCoA curriculum that is

divided into Stage 1 (CT1-3), Stage 2 (ST4-5) and Stage 3 (ST6-ST7) in a spiral curriculum that is both competency and time-based. This is also a proxy outcome measure in that advancement through these competency-based stages of training already include forms of assessment of proficiency in UGRA. Demographic information will be gathered from the participants to demonstrate their prior regional anaesthesia experience. This will factor in additional courses, qualifications and fellowships in relevant areas to account for inconsistencies in clinical exposure to ultrasound throughout training and as a practising anaesthetist (specifically, training level, courses attended, regional anaesthesia fellowships completed, and ultrasound-based fellowships completed).

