### 3.4 Phase 4 – Testing for content validity

To ensure all items in the assessment tool have the content that tests the domain we intend to test, following the pilot the amended test will be presented to the panel of 5 experts in regional anaesthesia, who will be asked to rate the suitability of ultrasound images and questions to performance of the block. This will be on a 4-point Likert scale (1 = definitely not suitable, 2 = probably not suitable, 3 = probably suitable, 4 = definitely suitable).

The content validity of each item will be calculated by dividing the number of experts who rated the item as suitable and very suitable (3 and 4 on the scale) by the total number of experts. Items found to be appropriate by a sufficiently high percentage of participants will be selected. For example, if 26 out of 40 (65%) participants rate an item as suitable or very

suitable then the lower 95% confidence limit for this proportion is 51%, indicating that more than 50% of experts are likely to find it appropriate.

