## 7.3 Plan of Analysis

We have taken advice from the Imperial College statistician, [name] [name].

The primary outcome will be analysed using a series of calculated indices and statistical tests. A difficulty index will be calculated by dividing the number of correct responses by the total number of responses, with a difficulty index  $<50\%$  considered sufficient to exclude an item from the test. Content validity will be calculated by asking an expert panel to rate items in the test on a 4-point scale as definitely not suitable, probably not suitable, probably suitable and definitely suitable. A validity index of  $> 0.78$  will be considered sufficient to include a question. Construct validity will be measured using a one-way analysis of variance (ANOVA)/Rasch modelling, internal reliability using Cronbach's alpha (with a value of 0.70 considered sufficient), and internal consistency using a split-test method.

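### Sections 3.4 and 7.3 give inconsistent content-validity rules: the 26-of-40 example cannot come from a panel of 5 and would fail the > 0.78 cut-off

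*Combined protocol and SAP*

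**What the plan says.** Section 1.1 gives content validity to experts: it "of the assessment tool will be verified by a panel of experts". Section 3.4 sets the number: "the amended test will be presented to the panel of 5 experts in regional anaesthesia". Each expert rates each item on a 4-point scale, and the index is found by "dividing the number of experts who rated the item as suitable and very suitable" (ratings of 3 or 4) by the number of experts.

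The next sentence of 3.4 changes the rater group and gives no cut-off: "Items found to be appropriate by a sufficiently high percentage of participants will be selected". The illustration that follows begins "if 26 out of 40 (65%) participants rate an item as suitable" (or very suitable) and concludes that the "lower 95% confidence limit for this proportion is 51%, indicating that more than 50% of experts are likely to find it appropriate". So within one sentence the 40 raters are participants and the inference is about experts.

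Section 7.3 also has an expert panel rate the items, without restating its size. It gives the only numeric cut-off: an index above 0.78 "will be considered sufficient to include a question". It mentions no confidence limit, and 3.4 does not mention 0.78. Section 7.3 lists this index among the analyses of the primary outcome.

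**The concern.** The two sections describe one decision, whether an item enters the final test, but differ on who is counted, how many raters there are and what level of agreement is enough. Section 3.4 presents an item at 0.65 as adequately supported, whereas 7.3 would not accept it. Section 3.4 also argues from a confidence limit, whereas 7.3 applies a cut-off to the index itself.

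Section 1.1 makes defensibility central to the tool: "There needs to be confidence in the processes used to construct the assessment tool". If the screen can be read in two ways, it could be settled after the expert ratings have been seen. The choice affects which items are taken into Phase 5.

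**Working it through.** **Inputs.** Panel of 5, index definition, and 26 of 40 with lower limit 51%: section 3.4. Cut-off > 0.78: section 7.3.

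**1. Reproduce the quoted 51%.** The proportion is 26/40 = 0.65. The plan does not name the interval method.

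- One-sided 95% exact (Clopper-Pearson), the 0.05 quantile of Beta(x, n − x + 1) = Beta(26, 15): 50.8%, which rounds to 51%.
- One-sided 95% Wald with continuity correction, p − 1.645√(p(1 − p)/n) − 1/(2n) = 0.65 − 1.645 × 0.0754 − 0.0125 = 0.5135: 51.35%, which also rounds to 51%.
- Other one-sided limits (Wald, Wilson, Agresti-Coull, Jeffreys) run from 52.0% to 52.6%.
- Two-sided 95% limits run from 48.3% (exact) to 50.2% (Wald).

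The 51% is therefore reproducible as a one-sided limit, by two of the methods tried.

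**2. Can the example arise from the panel?** With 5 raters the index is k/5 for k = 0 to 5: 0, 0.20, 0.40, 0.60, 0.80, 1.00. No k gives 0.65.

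**3. Does the example meet the cut-off?** 0.78 − 0.65 = 0.13, so it fails. With 40 raters, 0.78 × 40 = 31.2, so at least 32 are needed (32/40 = 0.80; 31/40 = 0.775 fails).

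**4. What the cut-off means for 5 raters.** 0.78 × 5 = 3.9, so at least 4 of 5.

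**5. Where the two lines of reasoning differ.** Apply both to the panel of 5, using the two methods that reproduce 51%:

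| Rated suitable | Index | > 0.78? | Lower limit, one-sided exact | Lower limit, one-sided Wald with correction | Above 50%? |
|---|---|---|---|---|---|
| 3 of 5 | 0.60 | No | 18.9% | 14.0% | No |
| 4 of 5 | 0.80 | Yes | 34.3% | 40.6% | No |
| 5 of 5 | 1.00 | Yes | 54.9% | 90.0% | Yes |

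For 4 of 5, the corrected Wald limit is 0.80 − 1.645 × √(0.16/5) − 0.10 = 0.406. The exact limit solves 5p⁴(1 − p) + p⁵ = 0.05, giving p = 0.343.

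The two approaches part at 4 of 5. The result depends somewhat on method: one-sided Wald without correction gives 50.6% there, but it gives 52.6% for 26 of 40 and so is not the method behind the quoted 51%. The two-sided exact limit for 4 of 5 is 28.4%.

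**The case against.** The best defence is that 26 of 40 is offered only as an example. It sets no threshold. Section 3.4 supplies the panel size and formula, and 7.3 the only numeric cut-off; together they give a workable rule of at least 4 of 5. On this view the example is a leftover. Much of this stands, and it is why the point is minor. It does not remove the inconsistency: the example is the only illustration in 3.4 of what counts as high enough, 7.3 would reject the item it presents, and the plan does not say that 7.3 takes precedence.

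A second defence is that the 40 are the pilot participants, of whom section 3.3 plans 35 to 50. Section 3.3 asks them about ease of understanding, ambiguous terms and missing content. No section gives them the content-validity rating.

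A reader might also infer more than the documents support:

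- *That 3 of 5 is left undecided because 0.60 is close to 0.65.* Section 3.4 does not treat 65% as adequate in itself; it argues from the lower limit. At 3 of 5 that limit is far below 50%, and 0.60 also fails > 0.78.
- *That the word sufficient in 7.3 leaves exclusion open.* Section 7.3 uses the same word for its difficulty and alpha thresholds, so the ordinary reading is a cut-off.
- *That 51% is an arithmetic error.* It is not, if it is a one-sided limit.
- *That the plan imposes a rule of a lower limit above 50% on the panel of 5.* It does not. The table shows only that the inference in the example cannot be carried over.

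**Conclusion.** Wrong as written, and minor. Sections 3.4 and 7.3 do not give one consistent inclusion rule. The 0.65 example is impossible with 5 raters and falls 0.13 short of the cut-off. At 4 of 5, the lowest result that passes 7.3, the inference that more than half of experts would agree does not hold by either method that reproduces the quoted 51%.

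That last comparison assumes the 51% is a one-sided limit from one of those two methods, since the plan names none. The mismatches with the panel size and with the cut-off need no such assumption.

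The effect is confined to one item screen before the main study. The curriculum matching in 1.1, the guideline review in 3.1 and the Delphi step in 3.2 are unaffected, so a reader should not conclude that content validity as a whole is unsupported.

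**What to change.** State one rater group, one panel size and one rule, in the same terms in 3.4 and 7.3. The authors need to say which group they meant.

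*If the panel of 5 and the > 0.78 cut-off are intended:* in 3.4, change participants to experts and delete the 26-of-40 example with its inference about more than 50%. In both sections write: an item is included if its content validity index from the 5 experts is > 0.78, that is, if at least 4 of 5 rate it 3 or 4; any confidence limit reported is descriptive only. This costs wording in two sections, with no new data and no extra experts.

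*If a larger rating group was intended:* correct the panel size in 3.4, say who the raters are, and replace the example with one that meets > 0.78 (for 40 raters, at least 32). This also costs the recruitment of the additional raters.

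In either case, settle the wording before the Phase 4 ratings are seen.

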### 7.3.1 Frequency of analyses

The primary analysis will take place when the pilot study recruitment is complete in phase 3. This will be used to guide the generation of the final version used in the next phase. Then the analysis of the phase 5 validation study will take place when recruitment for this test is complete. No interim analysis is planned.

### 7.3.2 Criteria for the termination of the trial

The study may be terminated early if the results of another study make it redundant, or on safety grounds.

### 7.3.3 Economic issues

There will be no formal economic analysis.

### 7.3.4 Data storage

All data will be stored in anonymised form and analysed on NHS Trust computers.

Data and all appropriate documentation will be stored for a minimum of 5 years after the completion of the study.

## 8. Regulatory Issues

### 8.1 Ethics Approval

The Study Coordination Centre has obtained approval from the **xxx** Research Ethics Committee (REC) and Health Regulator Authority (HRA). The study must also receive confirmation of capacity and capability from each participating NHS Trust before accepting participants into the study or any research activity is carried out. The study will be conducted in accordance with the recommendations for physicians involved in research on human subjects adopted by the 18th World Medical Assembly, Helsinki 1964 and later revisions.

### 8.2 Consent

Consent to enter the study must be sought from each participant only after a full explanation has been given, an information leaflet offered and time allowed for consideration. Signed participant consent should be obtained. The right of the participant to refuse to participate without giving reasons will be respected. All participants are free to withdraw at any time from the protocol without giving reasons.

### 8.3 Confidentiality

The Chief Investigator will preserve the confidentiality of participants taking part in the study and is registered under the Data Protection Act. Data will be pseudonymised.

Each participant will be identified by a unique sequential number identifier allocated to them and this information and all data collected will be stored in the master file in the Primary Investigator's locked office on the hospital site.

## 8.4 Indemnity

Imperial College Healthcare NHS Trust holds standard NHS Hospital Indemnity and insurance cover with NHS Resolution for NHS Trusts in England, which apply to this study.

## 8.5 Sponsor

Imperial College Healthcare NHS Trust will act as the main Sponsor for this study.

## 8.6 Funding

This study is unfunded

## 8.7 Audits

The study may be subject to inspection and audit by Imperial College Healthcare NHS Trust under their remit as sponsor and other regulatory bodies to ensure adherence to GCP and the UK Policy Frame Work for Health and Social Care Research.

## 9. Study Management

The trial will be managed by a Trial Management Group (TMG). The TMG will be chaired by a Chief Investigator and will include all members of the named research team (see Chief Investigators & Research Team Contact Details).

A study principal investigator will be responsible for identifying potential participants, seeking informed consent, collecting trial data and ensuring adherence to the trial protocol.

## 10. Publication Policy

We anticipate that the results will be published in a peer-reviewed journal and may be presented at a national and international conferences.

## 12. Appendix

The following link allows you to view sample question(s) that would be posed to the participants

[https://1drv.ms/u/s!AoKOa\\_qdcBwN7xRgYp6889QRs-qh?e=4pd9f2](https://1drv.ms/u/s!AoKOa_qdcBwN7xRgYp6889QRs-qh?e=4pd9f2)

All ultrasound images are taken from voluntary study team members or NHS patients. These images are fully anonymised and contain no staff and/or patient information and cannot be identified by anyone even study team members. Verbal consent has been gained from all volunteers and NHS patients explaining these images are used for educational purposes as is the nature of this assessment tool being developed.
